PROTOCOL NUMBER: OSU-19132

SYNOPSIS

Study Title	A Phase II Single Arm Trial of Ramucirumab with Pembrolizumab in EGFR Mutant Non-Small Cell Lung Cancer
Study Rationale	
Non-small cell lung cancer (NSCLC) is one of the most common and lethal cancers in the United States. Fifteen percent of these NSCLC patients have epidermal growth factor receptor (EGFR) driver mutations, which are associated with high response rates (>70%) to tyrosine kinase inhibitors (TKI) but low response rates (10%) to single agent immune checkpoint inhibitors (ICI) such as pembrolizumab (anti-PD1 monoclonal antibody (mAb)).[1-5] In addition, responses to TKIs are not durable due to acquired resistance.[6] Vascular endothelial growth factor (VEGF) has emerged as a potential pathway of interest for treatment in this patient population because EGFR mutant NSCLC is associated with increased VEGF expression.[7] Notably, VEGF induces tumor related angiogenesis and also has immune dysregulatory effects that impact dendritic cell (DC) maturation, myeloid derived suppressor cells (MDSC) proliferation, and T cell PD-1 expression.[8-11] In clinical and preclinical studies, VEGFR inhibitors reverse this immune dysregulation and may work in synergy with ICI to enhance immune response.[12-14]
 
Given the lack of durable responses to first line therapy in EGFR mutant NSCLC, development of tolerable and effective second line therapies is imperative. Two phase 3 trials demonstrated potential clinical importance of VEGF inhibitors for EGFR mutant patients receiving ICI. IMPower150 demonstrated progression-free survival advantage for carboplatin and paclitaxel with bevacizumab (anti-VEGF mAb) and atezolizumab (anti-PDL1 mAb) whereas IMPower130 demonstrated no survival difference for carboplatin, nab-paclitaxel, and atezolizumab without the addition of bevacizumab.[15-17] These results suggest a key role of anti-VEGF in combination with ICI in the EGFR mutant population and this combination may obviate the need for chemotherapy. Chemotherapy toxicity was significant in both IMPower trials – up to 55% of patients experienced grade 3-4 toxicity, most of which was attributable to carboplatin and paclitaxel (neuropathy, nausea, and pancytopenia).[16]

IRB Protocol Number: 2019C0145
IRB Approval date: 06/10/2022
Version: 05/06/2022

PROTOCOL NUMBER: OSU-19132

	
To evaluate the clinical efficacy of this combination, we propose a phase II single arm trial of ramucirumab (anti-VEGFR mAb) and pembrolizumab (anti-PD1 mAb) for EGFR mutant NSCLC patients who have progressed on at least one EGFR TKI. The primary endpoint will be response rate and the secondary endpoints will be safety, tolerability, and survival. We anticipate that the combination of ramucirumab and pembrolizumab will be associated with a higher response rate ($\geq 25\%$) than observed responses with single agent ICI ($\sim 10\%$). We will perform exploratory correlative studies to evaluate the immune cell activation profiles with combination therapy.

Primary Objective	To evaluate response rate of the combination of ramucirumab and pembrolizumab in EGFR mutant NSCLC.
Secondary Objectives	To evaluate safety, tolerability, and survival for patients receiving ramucirumab and pembrolizumab.
Correlative Studies	
Exploratory objectives: To characterize predictive immunologic biomarkers of response in tissue and peripheral blood of patients receiving R+P combination therapy
 
Exploratory Correlative Endpoints:
 
1) Baseline tumor immunoprofile by IHC, including tumor infiltrating lymphocytes and T cell receptor (TCR) immunosequencing (immunoSEQ) and relationship to clinical outcomes, including response rate.2) Circulating immune cell profiles in response to treatment and in relation to clinical response using 10-color 65 marker multiplex CyTOF profile on peripheral blood samples.3) Circulating VEGF at baseline, after treatment and at progression to evaluate correlation with clinical response.
Sample Size	Minimum 13 patients, maximum 34 patients
Study Design	Agents: Ramucirumab, Pembrolizumab

IRB Protocol Number: 2019C0145
IRB Approval date: 06/10/2022
Version: 05/06/2022

PROTOCOL NUMBER: OSU-19132

	
Tumor type: EGFR mutation positive NSCLC
 
The proposed study will be an open-label single arm phase II trial of ramucirumab and pembrolizumab (R+P) in EGFR mutant NSCLC after progression on tyrosine kinase inhibitors (TKIs). Patients are required to receive at least one TKI (erlotinib, gefitinib, afatinib or osimertinib). Post-TKI chemotherapy is also permitted.
 
Each treatment cycle will be 21 days; patients will receive ramucirumab 10 mg/kg IV and pembrolizumab 200 mg IV and on day 1. Dosing of ramucirumab and pembrolizumab is based on prior phase 1 testing of the combination. A two-stage design will be utilized to minimize exposure to combination therapy if there is limited efficacy. The initial stage will enroll 13 patients; if ≥ 1 patient has a confirmed response, the study will continue and enroll an additional 21 patients for a total of 34 patients.
 
Response will be assessed using RECIST (RECIST 1.1 and iRECIST). Imaging will be performed every 6 weeks/2 cycles to assess response. Patients with clinical benefit may continue therapy beyond progression for up to 2 cycles – if progressive disease confirmed on repeat imaging, therapy would be discontinued. Toxicity will be assessed using CTCAE v5.0. Progression free survival will be assessed using RECIST and will be assessed starting from date of study enrollment.
 
Blood samples tissue will be collected at baseline (day 1, cycle 1), cycle 3 day1 (approx. 6 weeks), and at study discontinuation (or progression). Archival tissue will be requested at enrollment for correlative studies.

Duration of Treatment	Patients may continue to receive study treatment (R+P) until radiographic documentation of disease progression, the occurrence of unacceptable toxicity or of the occurrence of other withdrawal criteria. If either drug is discontinued due to toxicity, the other drug may be continued.
Inclusion /Exclusion Criteria	
Inclusion Criteria:
 
1. Adult patients aged ≥ 18 years

IRB Protocol Number: 2019C0145
IRB Approval date: 06/10/2022
Version: 05/06/2022

PROTOCOL NUMBER: OSU-19132

	
2. Histologically confirmed recurrent or metastatic non-small cell carcinoma of the lung with sensitizing EGFR mutations. Exon 20 resistance mutations will not be permitted but uncommon sensitizing mutations are allowed.3. Prior Systemic Anticancer Therapy: Neo/adjuvant therapy or prior therapy for locally advanced disease will be permitted. Patients with prior exposure to PD/PD-L1 inhibitors will be excluded. No limit on prior EGFR TKIs (erlotinib, gefitinib, afatinib, dacomitinib or osimertinib). Prior chemotherapy for metastatic disease is permitted only. A 7 day washout period or four half-lives after the last treatment dose, whichever is longer, is required for TKI. A 4 week washout is required for cytotoxic chemotherapy.4. Measurable disease per RECIST criteria5. ECOG performance status of 0-16. Adequate organ function, hematologic, hepatic, renal and coagulation parameters as defined in the protocol.7. Because the teratogenicity of ramucirumab is not known, the patient, if sexually active, must be postmenopausal, surgically sterile, or using effective contraception (hormonal or barrier methods).8. Female patients of childbearing potential must have a negative serum pregnancy test within 72 hours prior to first dose of protocol therapy.
--	--

Exclusion Criteria

1. Active autoimmune disease that has required systemic treatment in the past 2 years (i.e. with use of disease modifying agents, corticosteroids or immunosuppressive drugs). Replacement therapy (eg., thyroxine, insulin, or physiologic corticosteroid replacement therapy for adrenal or pituitary insufficiency, etc.) is not considered a form of systemic treatment.
2. Known active chronic infections – HIV/AIDS, known active Hepatitis B or C. Known history of Hepatitis B (defined as Hepatitis B surface antigen [HBsAg] reactive) or known active Hepatitis C virus (defined as HCV RNA [qualitative] is detected) infection. Note: no

IRB Protocol Number: 2019C0145
IRB Approval date: 06/10/2022
Version: 05/06/2022

PROTOCOL NUMBER: OSU-19132

	
testing for Hepatitis B and Hepatitis C is required unless mandated by local health authority.
 
3. Cirrhosis (Child-Pugh B or worse) or cirrhosis with history of hepatic encephalopathy or clinically meaningful ascites resulting from cirrhosis.
 
4. Prior exposure to ramucirumab.
 
5. Has received prior therapy with an anti-PD-1, anti-PD-L1, or anti-PD-L2 agent or with an agent directed to another stimulatory or co-inhibitory T-cell receptor (eg, CTLA-4, OX-40, CD137).
 
6. Any Grade 3-4 GI bleeding within 3 months prior to first dose of protocol therapy.
 
7. History of deep vein thrombosis (DVT), pulmonary embolism (PE), or any other significant thromboembolism (venous port or catheter thrombosis or superficial venous thrombosis are not considered “significant”) during the 3 months prior to first dose of protocol therapy.
 
8. Patients receiving dipyridamole, clopidogrel, or similar agents. Once-daily aspirin use (maximum dose 325 mg/day) is permitted.
 
9. Uncontrolled CNS metastases. Patients with treated brain metastases are eligible if they were clinically stable with regard to neurologic function, off steroids after cranial irradiation (whole brain radiation therapy, focal radiation therapy, and stereotactic radiosurgery) ending at least 2 weeks prior to first dose of study treatment, or after surgical resection performed at least 28 days prior to first dose of study treatment. The patient must have no evidence of Grade ≥ 1 CNS hemorrhage based on pretreatment MRI or IV contrast CT scan (performed within 28 days before first dose of study treatment). Note: Patients who received systemic therapy that adequately and appropriately treated CNS metastases, including tyrosine kinase inhibitors, are eligible provided that CNS disease control is confirmed by pretreatment MRI within 28 days of receiving first dose of study treatment.
 
10. Hemoptysis (defined as bright red blood or $\geq 1/2$ teaspoon) within 2 months prior to first dose of protocol therapy or with radiographic evidence of intratumor cavitation or has radiologically documented evidence of major blood vessel invasion or encasement by cancer.

--	---

IRB Protocol Number: 2019C0145
IRB Approval date: 06/10/2022
Version: 05/06/2022

PROTOCOL NUMBER: OSU-19132

	
11. Uncontrolled or poorly-controlled hypertension (>160 mmHg systolic or > 100 mmHg diastolic for >4 weeks) despite standard medical management.12. Any arterial thromboembolic events, including but not limited to myocardial infarction, transient ischemic attack, cerebrovascular accident, or unstable angina, within 6 months prior to first dose of protocol therapy.13. Major surgery within 28 days or device placement within 7 days prior to the first dose of protocol therapy. Patient has elective or planned major surgery to be performed during the course of the clinical trial.14. Serious or non-healing wound, ulcer, or bone fracture within 28 days of study treatment.15. Prior history of GI perforation/fistula (within 6 months of first dose of protocol therapy) or risk factors for perforation.16. Small cell or mixed (small cell/non-small cell) lung cancer17. Pregnancy or breastfeeding.18. Has received a live vaccine within 30 days prior to the first dose of study drug. Examples of live vaccines include, but are not limited to, the following: measles, mumps, rubella, varicella/zoster (chicken pox), yellow fever, rabies, Bacillus Calmette–Guérin (BCG), and typhoid vaccine. Seasonal influenza vaccines for injection are generally killed virus vaccines and are allowed; however, intranasal influenza vaccines (eg, FluMist®) are live attenuated vaccines and are not allowed.19. History of (non-infectious) pneumonitis that required steroids or has current pneumonitis.20. History or current evidence of any condition, therapy, or laboratory abnormality that might confound the results of the study, interfere with the subject's participation for the full duration of the study, or is not in the best interest of the subject to participate, in the opinion of the treating investigator.21. Known psychiatric or substance abuse disorders that would interfere with cooperation with the requirements of the trial.22. Severe hypersensitivity (\geqGrade 3) to pembrolizumab and/or any of its excipients.23. Active infection requiring systemic therapy.24. Known history of active TB (Bacillus Tuberculosis).
--	---

IRB Protocol Number: 2019C0145
IRB Approval date: 06/10/2022
Version: 05/06/2022

PROTOCOL NUMBER: OSU-19132

Screening Assessments	Signed written informed consent Inclusion/Exclusion Criteria Demographics and medical history Pregnancy test (if applicable) Physical examination, ECOG, and vital signs Urine analysis Hematology (CBC, coagulation studies) Complete serum chemistry Assessment of disease status Concomitant medication
Treatment and Post-Treatment Assessments	
Cycle 1 , Day 1
 
Physical examination and vital signs Complete blood count with differential Complete clinical chemistry (including liver function tests) TSH - free T3 and T4 if abnormal Adverse events and concomitant medication
 
Cycle 1, Day 8
 
Physical examination and vital signs Complete clinical chemistry (including liver function tests) Urinalysis
 
Cycle 2 and Beyond
 
Physical examination and vital signs Complete blood count with differential Complete clinical chemistry (including liver function tests) TSH - free T3 and T4 if abnormal – repeat every 3rd cycle Urine analysis Pregnancy test (if applicable)
 
Assessment of disease status:
 
• CT scans (disease evaluation will be done according to irRECIST and RECIST 1.1) 
Adverse events and concomitant medication

IRB Protocol Number: 2019C0145
IRB Approval date: 06/10/2022
Version: 05/06/2022

PROTOCOL NUMBER: OSU-19132

	
Final Visit
 
Physical examination and vital signs
 
Complete blood count with differential
 
Complete clinical chemistry (including liver function tests)
 
Assessment of disease status
 
Adverse events and concomitant medication

Response	CT scans will be used for tumor assessment, at baseline and then at 6 week intervals. Patients who achieve stable disease, partial response (PR), or complete response (CR) per RECIST v.1.1 criteria will continue therapy until disease progression. Patients with confirmed disease progression by RECIST will be discontinued.
Safety Variables & Analysis	The safety and tolerability of ramucirumab and pembrolizumab will be evaluated by assessment of drug related toxicities, adverse event (AE) reports, physical examinations, and laboratory safety evaluations. Common Terminology Criteria for Adverse Events (CTCAE) v5.0 will be used for grading of AEs. Investigators will provide their assessment of causality as 1) unrelated, 2) possibly related, or 3) probably or definitely related for all AEs.
Statistical Analysis	
The primary study objective is to assess the overall response rate (ORR) of ramucirumab and pembrolizumab. The study will use Simon's two-stage design. Response rate with single agent IO is around 10% and we would consider a response rate of at least 25% to be interesting for further study. The initial stage will include 13 patients; the trial will be terminated if there are no responses. If the trial goes on to the second stage, an additional 21 patients will be included for a total of 34 patients studied.
 
Secondary objectives involve evaluating safety and tolerability and estimating PFS and overall survival. Descriptive statistics will be calculated for these outcomes and Kaplan-Meier curves will be calculated to estimate PFS and OS. Patients who have reached the end of the study but not progressed will be considered censored at the last documented date of contact. Estimates from this analysis will be used as preliminary data to inform future research.

IRB Protocol Number: 2019C0145
IRB Approval date: 06/10/2022
Version: 05/06/2022

PROTOCOL NUMBER: OSU-19132

LIST OF ABBREVIATIONS AND DEFINITIONS OF TERMS

ADR	Adverse Drug Reaction
AE	Adverse event
ALT (SGPT)	Alanine aminotransferase
ANC	Absolute neutrophil count
APC	Adenomatous polyposis coli
API	Active pharmaceutical ingredient
AST (SGOT)	Aspartate aminotransferase
AUC	Area under the curve
BMI	Body mass index
BSA	Body surface area
BUN	Blood urea nitrogen
BW	Body weight
CBC	Complete blood count
CI	Confidence interval
CK	Creatine kinase
CNS	Central nervous system
CR	Complete response
CRF	Case report form
CRO	Contract research organisation
CTCAE	Common terminology criteria for adverse events
CT Scan	Computed Tomography Scan
CYP450	Cytochrome P450
DCR	Disease control rate
DLT	Dose-limiting toxicity
DNA	Desoxyribonucleic acid
ECG	Electrocardiogram
ECOG	Eastern Cooperative Oncology Group
EOT	End of treatment
FU	Follow-up
GCP	Good Clinical Practice
GI	Gastrointestinal
GLP	Good laboratory practice
h	Hour
HR	Hazard ratio
IA	Interim analysis
IMP	Investigational medicinal product
INR	International normalized ratio
IRB	Institutional review board
ITT	Intent to treat
i.v.	Intravenous
KRAS	Kirsten Rat sarcoma
LDH	Lactate dehydrogenase
m ²	Square metre (body surface area)

IRB Protocol Number: 2019C0145
IRB Approval date: 06/10/2022
Version: 05/06/2022

PROTOCOL NUMBER: OSU-19132

mg	Milligram
min	Minute
mL	Millilitre
MRI	Magnetic resonance imaging
MTD	Maximum tolerated dose
NCI	National Cancer Institute
ORR	Overall response rate
OS	Overall survival
PD	Progressive disease
PFS	Progression-free survival
PO	Per oral
PR	Partial response
PTT	Partial thromboplastin time
RECIST	Response Evaluation Criteria In Solid Tumors
SAE	Serious adverse event
SD	Stable disease
SADR	Serious adverse drug reaction
SUSAR	Suspected unexpected serious adverse reaction
TSH	Thyroid Stimulating Hormone
TPP	Time to progression
UNL	Upper normal limit
WBC	White blood cell count

IRB Protocol Number: 2019C0145
IRB Approval date: 06/10/2022
Version: 05/06/2022

PROTOCOL NUMBER: OSU-19132

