3.1.2 Timing of Dose Administration

Trial treatment should be administered on Day 1 of each cycle after all procedures/assessments have been completed as detailed on the Trial Flow Chart (Section 6.3). Trial treatment may be administered up to 3 days before or after the scheduled Day 1 of each cycle due to administrative reasons.

All trial treatments will be administered on an outpatient basis. Ramucirumab will be administered first followed by pembrolizumab.

Ramucirumab 10 mg/kg will be administered as an IV infusion every 3 weeks. Administer initial infusion over 60 minutes; if tolerated, may administer subsequent infusions over 30 minutes starting with cycle 2. Given the variability of infusion pumps from site to site, a window of -5 minutes and +10 minutes is permitted (i.e., infusion time is 30 minutes: -5 min/+10 min).

Pembrolizumab 200 mg will be administered as a 30 minute IV infusion every 3 weeks. Sites should make every effort to target infusion timing to be as close to 30 minutes as possible. However, given the variability of infusion pumps from site to site, a window of -5 minutes and +10 minutes is permitted (i.e., infusion time is 30 minutes: -5 min/+10 min).

The Pharmacy Manual contains specific instructions for the preparation of the pembrolizumab infusion fluid and administration of infusion solution.

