6.1.2 Laboratory Assessments

Safety blood samples include complete blood count, clinical chemistry, including liver function test, and coagulation.

IRB Protocol Number: 2019C0145
IRB Approval date: 06/10/2022
Version: 05/06/2022

PROTOCOL NUMBER: OSU-19132

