6.3 Schedule of Study Events

The Schedule of Study Events is shown in Table 4**Table 4**.

PROTOCOL NUMBER: OSU-19132

Table 4. Schedule of Study Events

Assessments	Screening/ Baseline			Cycle 1*	Cycle 1	Cycle 2	Cycle 2	Cycle 3 +	End of Treatment
Visit window [days]	Within 28 days	Within 10 days	Within 7 days	Day 1	Day 8	Day 1	Day 8	Day 1	30 days
						+/- 3 days		+/- 3 days	± 14 days
Informed consent ¹	X								
Inclusion and exclusion criteria		X							
Demographics		X							
Medical History ²		X							X
Pregnancy test (if applicable) ³		X						X	
Vital signs and weight ⁵		X		X	X	X	X	X	X
Physical examination and ECOG			X	X	X	X	X	X	X
Urine analysis ⁶		X		X	X	X	X	X	X
Hematology ⁷		X		X				X	X
Coagulation studies ⁸		X						X ⁷	
Complete Serum chemistry ⁹		X		X	X	X	X	X	X
TSH ¹⁰		X						X ⁹	
Peripheral blood correlative studies ¹¹				X				X ¹¹	X
Tumor biopsy ¹¹	X								X
Assessment of disease status ¹²	X							X	X
Ramucirumab dosing				X		X		X	
Pembrolizumab dosing				X		X		X	
Adverse event assessment				X		X		X	X
Concomitant Medication		X		X		X		X	X

Study Assessment Footnotes

PROTOCOL NUMBER: OSU-19132

* Each treatment cycle is 21 days

¹ Prior to the first study-specific assessments

² Medical history includes baseline symptoms as well as a detailed history of prior cancer therapies including start and stop dates, disease progression during or after therapy, as well as discontinuations due to intolerance or any other serious illness.

³ Applicable for women of childbearing potential. Serum β -HCG test within 14 days before the first dose of study drug.

⁴ Urine pregnancy test on day 1 of cycle 1 to confirm pregnancy status prior to treatment. Repeat urine pregnancy testing for women of childbearing potential every 9 weeks or if pregnancy is suspected. Positive urine pregnancy testing will require confirmation with serum pregnancy testing.

⁵ Vital signs: Weight, blood pressure, pulse and temperature

⁶ Urine analysis will include appearance, color, glucose, hemoglobin, ketones, pH, and protein. Microscopy will only be performed if clinically indicated. Urine dipstick protein $> 1+$ will require 24 hour urine collection for urine protein assessment. 24 urine collection will include measurement of both protein and creatinine.

⁷ Hematology: Complete blood count including differential is required. WBC differential may be automated or manual as per institutional standards.

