⁸ Coagulation studies will include PT/INR and PTT. These studies will be repeated every 3rd cycle or as needed (for patients on active anti-coagulation).

⁹ Complete Serum Chemistry includes: sodium, potassium, chloride, bicarbonate, BUN, creatinine, glucose, calcium, phosphate, magnesium, ALT, AST, alkaline phosphatase, total bilirubin, total protein, albumin.

¹⁰ TSH will be performed at baseline - free T3/free T4 to be checked if TSH is out of the normal range.

¹¹ Correlative studies (peripheral blood) will be drawn pre-treatment on cycle 1 day 1; cycle 3 day 1, and at final study visit. Tumor biopsy sample (archival) will be collected at study enrollment. Optional tumor biopsy at progression if clinically indicated.

¹² Disease status will be measured by CT scan every 6 weeks (+/- 7 days) for the first 6 months and then every 12 weeks and as clinically indicated. Baseline imaging within 28 days of study initiation.

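### Table 4 schedules no blood count at cycle 2 day 1, although the synopsis lists one from cycle 2 onward, so dose 2 can be given with no count since before dose 1

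*Combined protocol and SAP*

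**What the plan says.** The synopsis, under Treatment and Post-Treatment Assessments, has a block for cycle 2 and beyond that includes "Complete blood count with differential Complete clinical chemistry (including liver function tests) TSH - free T3 and T4 if abnormal – repeat every 3rd cycle". The only interval in that run of text belongs to the thyroid test. The synopsis list for cycle 1 day 8 has no blood count; its laboratory items are "Complete clinical chemistry (including liver function tests) Urinalysis".

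Table 4 (Section 6.3) marks Hematology at four places: screening (within 10 days), cycle 1 day 1, day 1 of cycle 3 onward, and end of treatment. Cycle 1 day 8, cycle 2 day 1 and cycle 2 day 8 are blank. In the same table, serum chemistry and both drugs are marked at cycle 2 day 1. Footnote 7, attached to Hematology, gives content and no timing: "Complete blood count including differential is required".

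Two sections make Table 4 the operative schedule. Section 3.1.2 states "Trial treatment should be administered on Day 1 of each cycle after all procedures/assessments have been completed as detailed on the Trial Flow Chart". Section 6.3.2 lists hematology for the treatment phase and refers to Table 4 for when it is done. Section 6.1.2 classes the count as a safety test: "Safety blood samples include complete blood count, clinical chemistry, including liver function test, and coagulation".

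**The concern.** The synopsis and the visit schedule give different answers to a simple question: is a blood count due before the second dose? A site that follows Table 4 complies with the protocol and still omits a test that the synopsis lists.

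What is at stake is early detection of a cytopenia. Sections 7.1 and 7.2 say that the combination's safety profile is not yet fully known. If no count is taken at cycle 2 day 1, a symptom-free fall in neutrophils, platelets or hemoglobin after dose 1 could go unseen when dose 2 is given. It would then not trigger the general rules that might apply: the ramucirumab hold for other toxicities in Section 7.1.2, or the row for other immune-related events in Table 5. It could also be missing from the maximum-grade toxicity tables planned in Section 9.4.2, where safety is a secondary endpoint.

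**Working it through.** The plan states no figure to reproduce. The check has two parts: whether the blank looks deliberate, and how long the gap is.

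**1. Is the blank deliberate?**

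Ten rows of Table 4 are marked at both cycle 1 day 1 and day 1 of cycle 3 onward: vital signs, physical examination, urine analysis, hematology, serum chemistry, correlative blood, ramucirumab, pembrolizumab, adverse events and concomitant medication. Eight of the ten are also marked at cycle 2 day 1. The exceptions are:

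- Correlative blood, which footnote 11 restricts to named visits: "Correlative studies (peripheral blood) will be drawn pre-treatment on cycle 1 day 1; cycle 3 day 1, and at final study visit".
- Hematology, which no text restricts.

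The synopsis block for cycle 2 onward pools several visits, and some of its items are not marked at cycle 2 day 1 either. Each of those has its own interval:

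- CT, footnote 12: "Disease status will be measured by CT scan every 6 weeks (+/- 7 days) for the first 6 months".
- Pregnancy test, footnote 4: "Repeat urine pregnancy testing for women of childbearing potential every 9 weeks or if pregnancy is suspected".
- TSH: every third cycle, in the synopsis and in Section 6.3.2.

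Hematology has no such interval. The synopsis also does not list counts at every visit: it omits one at cycle 1 day 8, as Table 4 does.

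**2. How long is the gap?**

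Inputs: a 21-day cycle (Table 4); a dosing window of 3 days either side of the scheduled day 1 (Section 3.1.2), taken here as fixed to the planned calendar day; and end of treatment 30 days after the last dose, plus or minus 14 (Section 3.1.4). Cycle 1 day 1 is the reference. Scheduled doses then fall on days 1, 22 and 43, and the cycle 1 day 1 count precedes dose 1.

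*Table 4 as written*

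- Age of the last scheduled count at dose 2: 22 − 1 = 21 days; range 21 − 3 = 18 to 21 + 3 = 24.
- Cycle 1 day 1 to the next count, at cycle 3 day 1: 43 − 1 = 42 days; range 42 − 3 = 39 to 42 + 3 = 45. Two doses are given in between.
- Patient who stops after dose 2, cycle 1 day 1 to the end-of-treatment count: 21 + 30 = 51 days; low 18 + 16 = 34, high 24 + 44 = 68.

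*With Hematology marked at cycle 2 day 1*

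- Count on the day of dose 2.
- Cycle 2 day 1 to cycle 3 day 1: 42 − 21 = 21 days; low 39 − 24 = 15, high 45 − 18 = 27.
- Dose 2 to end of treatment for a patient who stops there: 30 days; range 30 − 14 = 16 to 30 + 14 = 44.

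**The case against.** **The synopsis block is a pooled list.** A count that starts at cycle 3 still falls within cycle 2 and beyond, and the protocol says that Table 4 governs timing. On that reading there is no strict contradiction. It is a possible reading, but the other pooled items that Table 4 leaves unmarked at cycle 2 day 1 each have an interval that explains it. The count has none.

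**The synopsis is an imperfect yardstick.** It lists TSH at cycle 1 day 1, where Table 4 has no mark. It omits urine analysis at cycle 1 day 1 and at the final visit, where Table 4 marks it. It never separates out the cycle 2 day 8 visit. This stands, and it lowers confidence about which source is wrong.

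**The eight-of-ten pattern is weaker than it sounds.** Only two of the eight rows are laboratory rows, urine analysis and chemistry. Both are also marked on the two day-8 visits, so hematology is on a sparser schedule in any case. This is fair. It still does not explain why the count is skipped on a dosing day when it is taken before dose 1 and from dose 3 onward.

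**A mark may have been lost when the PDF was read.** Table 4 also shows no pregnancy test at cycle 1 day 1, although footnote 4 and Section 6.3.2 require one. A lost mark cannot be excluded. However, the Hematology row has its full set of cells, and the chemistry and dosing rows confirm which column is cycle 2 day 1.

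**The harm is remote.** Neither the ramucirumab rules nor Table 5 sets a count threshold for redosing. Examination, chemistry and adverse event assessment already take place at cycle 2 day 1, and unscheduled counts are allowed. All of this stands and is why the consequence is rated minor.

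**Conclusion.** The discrepancy is real. Followed as written, Table 4 leaves no scheduled blood count from before dose 1 until cycle 3 day 1, a span of 42 days (39 to 45) with two doses given. For a patient who stops after dose 2 the span is 51 days (34 to 68). The blank is more likely a slip than a choice, but the documents do not settle that, so confidence is medium.

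The effect is limited to safety monitoring and the descriptive adverse event tables. The response endpoint, the two-stage rule and the sample size are unaffected. The documents give no cytopenia rate for this regimen, so the number of events that might be missed cannot be estimated. The day counts assume that cycles run on schedule within the stated windows; dose delays would lengthen them. They also assume that no unscheduled count is taken.

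**What to change.** Mark Hematology at cycle 2 day 1 in Table 4. The schedule then agrees with the synopsis, and under Section 3.1.2 the count becomes one of the checks completed before dose 2. Adding an interval to the synopsis would also remove the mismatch, but it would leave dose 2 uncovered.

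The cost is one mark in the table and one extra count for each patient who reaches cycle 2: at most 34, or at most 13 if the trial stops at stage 1. Chemistry is already drawn that day, so no extra visit or needle stick is needed. Under Section 11.3.2 the test may be billed to the patient as routine laboratory work.
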